^a Participants who discontinue from the study prior to study completion should complete the ED visit procedures.

^b Screening will be performed within 28 days of the first dose being administered.

^c All participants will remain in the CRU until completion of Day 4 procedures.

^d Hematology and clinical chemistry sample to be taken in the morning.

^e A standard urine test strip/dipstick may be used.

^f A serum beta-hCG test will be performed in all female participants, except in female participants with confirmed hysterectomy.

^g A single 12-lead ECG will be recorded in the supine position after 5 minutes of rest.

^h randomization will occur during first period only.

ⁱ Doses are planned to be administered as follows in each period:

- Period 1-Fed standardized high fat meal to start 30 minutes prior to dose administration
- Period 2-Fasted at least 8-hours predose with a standardized high fat meal administered 30 minutes post dose
- Period 3-Fasted at least 8-hours predose with a standardized high fat meal administered 1 hour post dose

Periods will be separated by a washout of at least 1 week. The meals administered in all treatment periods should be consumed within 30 minutes. The exact time study drug is administered will be recorded.

^j In each treatment period, on Day 1, PK samples will be collected at time zero (predose) and at approximately 1, 2, 4, 6, 8, and 12 hours after dosing. One PK sample will be taken at 24, 48, and 72 hours postdose (Days 2, 3, and 4), and if applicable, at the ED Visit. PK sample collection times are provided as a guidance and may be modified based on clinical needs. Actual dates and times of sample collection must be recorded. The following time collection intervals are proposed: predose samples may be obtained between waking up and dosing.

Postdose samples may be obtained within $\pm 5\%$ of the scheduled collection time. The $\pm 5\%$ time window also applies to the start and end times of urine collection intervals. Post-assay remainder PK plasma samples may be stored for metabolite identification.

^k Urine collection interval is 0 to 24 hours postdose. The total urine volume of the 0- to 24-hour collection will be recorded.

Table 2-3 **Study Schedule Protocol J2D-MC-CVAA: Part B (MAD)-Cohort 7**

	S	Treatment/In CRU								Post treatment	ED ^a
		-1	1	2	3	5	8	14	15		
Study Day	≤28									23	
Visit Window (days)										±2	
Visits	1^b									3	
CRU admission		X									
CRU discharge									X		

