An additional cohort (Cohort 10) will assess the effect of timing of food on LY3526318 PK in 8 female participants. All participants in this cohort will receive 100 mg LY3526318 with standardized high fat meal in an open-label, 3-way crossover manner (meal administered prior to dose, at 30 minutes and at 1 hour post dose; Table 2-2). Participants receiving meals post dose administration will receive their dose after an approximately 8-hour fast. Periods will be separated by a washout period of at least 1 week.

Participants will return to the CRU for a final follow-up visit approximately 9 days after study drug administration or after the fed-state dose for female participants in the 100- and 400-mg cohorts.

Part B - MAD

The multiple-ascending doses of LY3526318 or placebo will be administered, at planned dose levels of 100, 400, and 1000 mg, once daily for 14 days in 3 cohorts of 8 female participants each. It is likely that 1 or more dose levels in Part B may exceed the approximate 10x margin to the projected NOAEL-equivalent exposures for males; for this reason, only female participants will be enrolled in Part B. The planned dose levels may be updated following a review of safety and PK data from Part A and they will not exceed those studied in Part A.

The first cohort of Part B will be administered LY3526318 following a review of Part A safety and PK data. Dose escalations to subsequent cohorts may occur after review of safety data and available PK data through 14 days from at least 6 participants in the prior cohort.

Following a screening period of up to 28 days, eligible participants will be confined to the CRU from Day - 1, until all study assessments are completed on Day 15. Within each cohort, participants will be randomly assigned to receive LY3526318 or placebo in a 6:2 ratio, except for Cohort 10; where all subjects will receive LY3526318 in all 3 periods in a fixed sequence.

LY3526318 or matching placebo is planned to be administered in an 8-hour fasting state once daily for 14 days. However, following a review of the food effect data from Part A, all doses may be administered with food.

Participants will return to the CRU for a final visit on Day 23.

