6.2 Randomization

A randomization schedule was generated by the EDS Biostatistics department of PRA for all cohorts except Cohort 10 according to the study specific Randomization Specifications created by then PRA biostatistician and approved by the Sponsor.

Part	Cohort	Period	Planned Treatment [#]	Actual Dose [#]	♀	♂	Stratified by sex
A	1a (sentinel)	1	10 mg LY3526318 or Placebo	10 mg	2		No
	1b	1	10 mg LY3526318 or Placebo	10 mg	6		No
	2	1	50 mg LY3526318 or Placebo	50 mg	4	4	Yes
	3	1	100 mg LY3526318 or Placebo	100 mg	8	4*	Yes
		2	100 mg LY3526318 or Placebo fed	30 mg	8		NA
	4	1	400 mg LY3526318 or Placebo	200 mg	8		NA
		2	400 mg LY3526318 or Placebo fed	200 mg	8		NA
	5	1	800 mg LY3526318 or Placebo	300 mg	8		NA
	6	1	1000 mg LY3526318 or Placebo	30 mg	8		NA
	10 (additional)	1	100 mg LY3526318 Fed standardized high fat meal to start 30 minutes prior to dose administration	100 mg	8		NA
		2	Fasted at least 8 hours predose with a standardized high fat meal administered 30 minutes post dose	100 mg			
		3	Fasted at least 8 hours predose with a standardized high fat meal administered 1 hour post dose	100 mg			
	11 (additional)	1	TBD mg LY3526318 or Placebo	NA	8		NA
B	7	1	100 mg LY3526318 or Placebo QD	30 mg	8		NA
	8	1	400 mg LY3526318 or Placebo QD	60 mg	8		NA
	9	1	Up to 1000 mg LY3526318 or Placebo QD	100 mg	8		NA
	12 (additional)	1	TBD mg LY3526318 or Placebo QD	NA	8		NA
	13 (additional)	1	TBD mg LY3526318 or Placebo QD	NA	8		NA
*) Doses may be adjusted based on data obtained in previous study cohorts, see actual dose column for the adjusted doses.							
*) As a result of exposures found in the interim PK data after Cohort 2 being higher than expected, it was decided not to dose male subjects with a 100 mg dose in Cohort 3 and therefore the number of subject in this cohort was also 8.							
NA=not applicable, TBD=to be determined.							

Replacement subjects will receive the same randomization number as the subject to be replaced increased by 1000 and will be administered the same.

In Cohorts 3 and 4 the female subjects will be dosed in a 2nd period in which they were to receive the same treatment under fed conditions. After evaluation of the interim PK results, it was decided to reduce the dose level of Period 2 for Cohort 3 to 30 mg under fed conditions.

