An additional cohort (Cohort 10) will assess the effect of food on LY3526318 PK in 8 female participants. All participants in this cohort will receive 100 mg LY3526318 with a standardized high fat meal in an open-label, 3-way one-sequence crossover manner (meal administered prior to dose, at 30 minutes and at 1 hour post dose; Table 2-2). Participants receiving meals post dose administration will receive their dose after an approximately 8-hour fast. Periods will be separated by a washout period of at least 1 week.

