16.2 Pharmacokinetic Summaries

16.2.1 Pharmacokinetic Concentrations

Plasma concentrations for LY3526318 below the quantifiable limit (BQL) will be set to $\frac{1}{2}$ lower limit of quantification (LLOQ) in the computation of descriptive statistics of concentration values. Descriptive statistics (number of subjects, arithmetic mean, standard deviation, coefficient of variation, median, minimum, maximum, geometric mean, and geometric CV) will be used to summarize the plasma concentrations by treatment at each scheduled time point. If over $\frac{1}{2}$ the subjects in a given cell have values BQL then the descriptive statistics will not be presented and will instead display as BQL for the mean and minimum. All other statistics except the maximum will be missing.

Linear and semi-logarithmic plots of the geometric mean plasma concentration versus scheduled sampling time will be presented by part showing all fasted treatments in a single figure.

Separate geometric mean linear and semi-logarithmic plots will show the effect of food given at the same dose (fed versus fasted) for the 30 mg and 200 mg cohorts, that is: Cohort 3 Period 2 and Cohort 6 Period 1 for 30 mg and Cohort 4 Periods 1 and 2 for 200 mg. Also separate geometric mean linear and semi-logarithmic plots will show the effect of food and the timing of food given at the 100 mg dose level (predose, 30 min postdose and 1 hour postpose and fasted) from Cohort 10 Periods 1-3 and Cohort 3 Period 1, respectively. These plots will show time in hours. The plots will match the summary table results and will not have an observation at a given time point if more than half of the subjects have values BQL.

For the multiple dose part, geometric mean profiles will be presented for all treatments in a single plot with a Day 1 and Day 14 profiles superimposed. In addition, linear geometric mean through plasma concentrations versus scheduled sampling time will be presented. These trough plots will include all trough concentrations from time zero on Day 1 up to 24 hours after dosing on Day 14.

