16.2.2.2 Food Effect

The effect of food and the timing of food will be graphically presented using box-plots showing AUC_{0-24} , C_{max} versus treatment. This will be done in separate plots for the following comparisons:

- 100 mg LY fasted, 100 mg LY QD (Day only), 100 mg LY fed (-30 min), 100 mg LY fed (+30 min), and 100 mg LY fed (+60 min)
- 30 mg LY fasted (Cohort 6 Period 1) and 30 mg LY fed (Cohort 3 Period 2)
- 200 mg LY fasted 200 mg LY fed (Cohort 4 Periods 1 and 2)

In addition, for the 200 mg dose level (i.e. Cohort 4 Periods 1 and 2), an analysis of variance (ANOVA) will be performed on AUC_{0-24} and C_{max} using the SAS PROC MIXED to estimate the geometric mean ratio and corresponding 90% CIs. Dose normalized PK parameters will be natural logarithm transformed prior to the analysis. The model will include fixed effects for food consumption status (fasted or fed) and a random effect for subject. From this model the back-transformed least-squares means (LSMeans) for each treatment and their ratio will be estimated. The ratio of least-squares geometric means between fed and fasted condition and the corresponding 90% CI will be presented.

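### Cohort 10 gives its three meal timings in one fixed period order, so its exploratory timing-of-food plots cannot separate meal timing from period

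*Protocol*

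**What the plan says.** **Order.** Protocol Table 2-2, footnote i, puts the meal that starts 30 minutes before dosing in Period 1. It then specifies "Period 2-Fasted at least 8-hours predose with a standardized high fat meal administered 30 minutes post dose" and places the meal 1 hour after dosing in Period 3. Footnote h adds that "randomization will occur during first period only".

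SAP 6.0 describes Cohort 10 as one "where all subjects will receive LY3526318 in all 3 periods in a fixed sequence", and SAP 6.2 calls it a "3-way one-sequence crossover manner". SAP 6.2 also states: "A randomization schedule was generated by the EDS Biostatistics department of PRA for all cohorts except Cohort 10".

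**Purpose and analysis.** SAP 6.0 says the cohort "will assess the effect of timing of food on LY3526318 PK in 8 female participants". In SAP 16.2.2.2, "The effect of food and the timing of food will be graphically presented using box-plots showing" AUC0-24 and Cmax by treatment. SAP 16.2.1 adds geometric mean profiles that "will show the effect of food and the timing of food given at the 100 mg dose level". The only food-effect model in the SAP is for Cohort 4 (200 mg), and SAP 9.4.3 rules out formal hypothesis testing.

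**Meal instructions.** Protocol 7.1 has the drug given 30 minutes after the start of the meal and forbids food for at least 4 hours after dosing in every case. Protocol 6.3.1 places the high-fat meal of the food-effect cohorts before dosing. The synopsis exempts only the second dose in those cohorts from the 8-hour fast.

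**The concern.** With one order for everyone, a difference between two meal timings is also a difference between two periods. Anything that changes from one period to the next would appear in the plots as an effect of meal timing: a change in the women over time, in clinic or assay conditions, or residual drug. Neither SAP 16.2.1 nor 16.2.2.2 says that reading the plots as timing effects assumes no period effect.

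The randomization row in Table 2-2 has nothing to allocate, because all 8 women receive active drug in the same order.

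At stake is what a reader may conclude from Cohort 10 about how soon after dosing a meal still alters exposure. No primary or secondary endpoint depends on it.

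The meal wording is a lesser matter. Taken literally, the 4-hour food rule in 7.1 forbids the meals that Periods 2 and 3 require. The synopsis exempts the second dose from fasting, whereas in Cohort 10 the first dose is the fed one and the second follows a fast.

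**Working it through.** The plan gives no power, effect-size or variance figure for Cohort 10, so there is none to reproduce. The check is whether the timing contrasts can be estimated, and how much of a period shift they carry.

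**Inputs.** 8 women and 3 periods (Protocol 5.1), so 24 observations. One sequence (Table 2-2 footnote i; SAP 6.0 and 6.2). Call the timings A (-30 min), B (+30 min) and C (+60 min). The effects are subject (8 columns), timing (2) and period (2).

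**Estimability, fixed order ABC for all.**
- Subject + timing: rank 10, residual df 24 - 10 = 14.
- Subject + timing + period: 12 columns, rank still 10. None of B-A, C-A or C-B is estimable once period is in the model.

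**Estimability, six orders plus ABC and BCA.**
- Subject + timing + period: rank 12, residual df 24 - 12 = 12. All three contrasts are estimable.

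**Period share in unadjusted geometric-mean contrasts.** The weight on each period is the proportion of women receiving one timing in that period minus the proportion receiving the other.
- Fixed order, B versus A: weights -1 (Period 1), +1 (Period 2), 0 (Period 3). The whole difference between the two periods enters: 100%.
- Six orders plus ABC and BCA: numbers of women in Periods 1, 2, 3 are A 3, 2, 3; B 3, 3, 2; C 2, 3, 3. B versus A has weights 0, +1/8, -1/8. The other two contrasts likewise have one +1/8, one -1/8 and one 0. The share is 1/8 = 12.5%.

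**Illustration at assumed shifts, with no true timing effect.** A between-period ratio g gives an apparent timing ratio of g in the fixed order and g^(1/8) in the balanced one.

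| Assumed period ratio g | Fixed order | Six orders + two |
|---|---|---|
| 1.05 | 1.05 | 1.006 |
| 1.10 | 1.10 | 1.012 |
| 1.20 | 1.20 | 1.023 |

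The 1/8 applies to geometric means; box-plot medians follow it only approximately.

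**Precision.** For the unadjusted summaries the contrast variance is SD² × (1/8 + 1/8) = 0.250 × SD² in either design. If period were fitted in the balanced design, it would be (16/63) × SD² = 0.254 × SD² for all three contrasts. The 90% CI factor is exp(t(0.95, df) × SD × √v), with t = 1.761 at 14 df and 1.782 at 12 df.

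| Assumed within-subject log-SD | Fixed order, no period (14 df, v = 0.250) | Balanced, period fitted (12 df, v = 0.254) |
|---|---|---|
| 0.20 | 1.193 | 1.197 |
| 0.25 | 1.246 | 1.252 |
| 0.30 | 1.302 | 1.309 |

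The SAP plans no such interval for Cohort 10. The table shows only that balancing costs almost nothing even if one were computed.

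**The case against.** The fixed order is disclosed, the cohort belongs to an unpowered pilot food assessment, and no timing estimate, interval or test is planned. Meals are standardized, dosing is in the unit, periods are at least a week apart, and a predose sample in each period would reveal residual drug. The only scale in the protocol for a food effect is 3- to 5-fold (5.5), well beyond the shifts illustrated.

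This limits the weight of the point but does not remove it. Unadjusted plots carry a period shift in full whether or not a model is fitted. Washout and predose samples address carryover, not other period effects. The 3- to 5-fold figure compares fed with fasted; differences between meal timings could be smaller.

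Cohorts 3 and 4 also run fasted then fed in fixed order. There, Protocol 7.4.1.1 makes the fed dose wait for data from higher-dose cohorts. No such condition is stated for Cohort 10.

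Three stronger readings are tempting, and the documents support none of them:
- *The timing results are wrong.* No period shift is shown or sized; the plots simply cannot rule one out.
- *The order has no safety basis.* Parts of Protocol 3.3 and 5.4 are redacted, and amendment (c), which added Cohort 10, lists a redacted change to 3.3. This cannot be judged from the public text.
- *The meal wording would mislead the site.* Protocol 5.1, Table 5-1 and Table 2-2 make the intended conduct clear, and 7.1 refers to doses as indicated and specified.

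The objection that redesign may come too late is strong. SAP 6.2 lists an actual dose of 100 mg for all three Cohort 10 periods but NA for additional Cohorts 11 to 13. The Cohort 10 eCRF is dated 22-Jan-2020 and the last SAP revision 26-Mar-2020. This suggests completed dosing without proving it.

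**Conclusion.** The point holds as a cheap improvement to an exploratory comparison. In Cohort 10, meal timing and period are completely confounded: no timing contrast is estimable with period in the model, and 100% of any between-period difference enters the planned profiles as an apparent timing effect. Spreading the 8 women over the six orders plus two suitable repeats would reduce that share to 12.5%.

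The confounding follows from the schedule alone and needs no assumption. Its practical size depends on a period shift that the documents do not give; the 5%, 10% and 20% cases and the log-SDs are assumptions. The point concerns comparisons among the three Cohort 10 timings only. The meal-wording conflicts are a minor correction and affect no endpoint.

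**What to change.** **If Cohort 10 has not been dosed:** use the Period 1 randomization step to allocate the 8 women to the six meal-timing orders plus two repeats, chosen so that each timing falls 2 or 3 times in each period (for example ABC and BCA). Six orders are preferable to a three-order Latin square, in which each timing always follows the same other timing, so carryover is not balanced. The planned plots need no new model. The cost is an 8-line allocation list, mixed meal timings on a clinic day, and 2 df if period is ever fitted. The women, treatments and visits stay the same. The sponsor should first confirm that no redacted safety reason requires the present order.

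**If dosing is complete:** state in SAP 16.2.1 and 16.2.2.2 that meal timing is confounded with period in Cohort 10 and that reading the plots as timing effects assumes no period effect. Keep any step that assigns participant numbers, because the Randomized Set (SAP 10.1) is defined by having a randomization number. The cost is a sentence in each section.

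**In either case, correct the wording:**
- In Protocol 7.1, except Cohort 10 Periods 2 and 3 from the dose-after-meal instruction and the 4-hour no-food rule.
- In Protocol 6.3.1, except the same two periods from the meal-before-dose statement.
- In the synopsis, limit the fasting exception to the second dose in Cohorts 3 and 4 and the Period 1 dose in Cohort 10. Naming the doses is safer than a general reference to fed doses, because SAP Table 3 labels all three Cohort 10 conditions as fed.

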3.1 Study Rationale

Study J2D-MC-CVAA is a first-in-human (FIH) study designed to evaluate safety, tolerability, and pharmacokinetics (PK) of oral LY3526318 in healthy participants. LY3526318 is a small molecule designed to inhibit transient receptor protein ankyrin 1 (TRPA1), a calcium-permeable nonselective cation channel, expressed by peripheral pain-sensing nociceptors, which play a pivotal role in generation of pain (Maatuf et al. 2019). A nonclinical efficacy pharmacology study using a formalin-induced flinch model in rats showed an analgesic effect after a single dose of LY3526318. The potential of LY3526318 to produce unwanted pharmacological effects associated with central nervous system (CNS), cardiovascular, or respiratory functioning was determined in rats and monkeys, and *in vitro* systems (see Section 3.2). These evaluations support advancing LY3526318 to a FIH study with the initial development focusing on chronic pain reduction.

3.2 Background

Chronic pain is a major health issue affecting the quality of life of millions of patients. Nonsteroidal anti-inflammatory drugs are the primary choice of drugs for chronic pain treatment; however, efficacy is limited in many patients. Opioids are potent but sedating and have addictive potential, relegating them to third- and fourth-line treatment options in chronic pain (Ko et al. 2019).

TRPA1's role in pain and inflammation and its localization in sensory neurons have been characterized (Bodkin and Brain 2011; Ückert et al. 2017). It evokes pain and an adverse response when administered exogenously (Berta et al. 2017; Demartini et al. 2017; Maatuf et al. 2019; Wang et al. 2019). Additionally there is genetic evidence for the contribution of TRPA1 to chronic pain.

TRPA1 antagonists are undergoing evaluation in clinical trials, where there is evidence of efficacy and safety (ODM-108, NCT02432664; GRC 17536, EU Clinical Trial Register 2012-002320-33).

The results of the general toxicology studies, the behavioral and cardiorespiratory safety pharmacology studies, the *in vitro* human ether-à-go-go channel assay, and the *in vitro* and *in vivo* genotoxicity/mutagenicity battery justify moving forward into human clinical studies.

The CNS safety pharmacology study in the rat and cardiovascular respiratory study (Study # 00926046) in monkeys showed no adverse findings up to the highest dose (300 mg/kg) of LY3526318 tested. No test article-related toxicity was seen at any dose in the 28-day repeat-dosing study in monkeys (Study # 00926044). CCI

3.3 Benefit/Risk Assessment

There is no benefit anticipated for healthy participants administered LY3526318.

CCI

Nonclinical toxicology and safety pharmacology studies with LY3526318 support the administration of LY3526318 to humans, for the primary objective of the planned study to evaluate safety and tolerability of LY3526318 in healthy participants.

More information about the known and expected benefits, risks, serious adverse events (SAEs) and reasonably anticipated adverse events (AEs) of LY3526318 is provided in the Investigator's Brochure ([Lilly 2019](#)).

Since LY3526318 has previously not been administered to humans, the study will be designed and conducted in accordance with the "*Guideline on Strategies to Identify and Mitigate Risks for First-in-Human Clinical Trials with Investigational Medicinal Products*" (EMEA/CHMP/SWP/28367/07 Rev.1 - July 2017).

Additional information on scientific rationale for the study design and justification for planned LY3526318 doses are provided in Sections [5.4](#) and [5.5](#), respectively.

Taking all these findings into consideration, no additional human safety pharmacology risks are expected for healthy participants in the FIH study of LY3526318.

4 Objectives and Endpoints

Table 4-1 shows the objectives and endpoints of the study.

Table 4-1 Objectives and Endpoints

Objectives	Endpoints
Primary (Part A)	
To evaluate safety and tolerability of LY3526318 in healthy participants following a single oral dose	
 • AEs • SAEs
Primary (Part B)	
To evaluate safety and tolerability of LY3526318 in healthy participants following multiple once-daily oral doses for 14 days	
 • AEs • SAEs
Secondary (Part A)	
To evaluate the plasma pharmacokinetics of LY3526318 in healthy participants following a single oral dose	
 • AUC • C_{max} • t_{max}
Secondary (Part B)	
To evaluate the plasma pharmacokinetics of LY3526318 in healthy participants following multiple once-daily oral doses for 14 days	
 • AUC • C_{max} • t_{max}
Exploratory (Part A)	
To explore the pharmacokinetics of LY3526318 in fed versus fasted conditions	
 • AUC • C_{max} • t_{max}
To explore the single-dose pharmacokinetics of LY3526318 in urine	
 • LY3526318 urine concentration • Amount of LY3526318 excreted in 24-hour urine

Abbreviations: AE = adverse event; AUC = area under the concentration versus time curve; C_{max} = maximum

observed drug concentration; SAE = serious adverse event; t_{max} = time to C_{max} .

5 Study Design

